5.2 Dexamethasone (Standard of care comparator)

5.2.1 Description

Dexamethasone is a synthetic corticosteroid and possesses glucocorticoid activity. It is indicated for intraarticular or soft tissue injection for: synovitis of osteoarthritis, epicondylitis, acute nonspecific tenosynovitis.

In its approved indication there use limitations for immunocompromised individuals, pregnant females, persons with allergy to steroids, individuals with systemic fungal infections, and individuals with cerebral malaria. It is contra-indicated in systemic fungal infections, and hypersensitivity to any component of this product, including sulfites.

5.2.2 Treatment regimen

Dexamethasone will be used within its labeled indication for this study: intra-articular or soft tissue injection for: synovitis of osteoarthritis, epicondylitis, acute nonspecific tenosynovitis. It is the active comparator in this study.

Dexamethasone will be administered as a peritendonous soft tissue injection of 1 mL of dexamethasone sodium phosphate (4mg/mL) and 0.5 mL (5mg) of 1% lidocaine

Patients will be followed at the initial office visit, 4-weeks, 8-weeks, 12-weeks, and 6 months post injection to determine clinical response. A second injection can be given only once if the patient desires due to no clinical response at the 4 or 8-week follow-up.

5.3 Lidocaine (Standard of care co-administered anesthetic)

Lidocaine is a local anesthetic of the amide type, and will be used within its labeled indication for this study: production of local or regional anesthesia by infiltration techniques such as percutaneous injection. It will be administered as 0.5 mL (5mg) of 1% lidocaine in combination with both the investigational agent, ketorolac injection, and the standard of care therapy, dexamethasone injection.

5.5 Method for Assigning Subjects to Treatment Groups

When a patient is enrolled and consented into the study a random envelope (labeled with an identification number) will be opened and in it will contain the group that the patient is randomized to: steroid or ketorolac. Envelopes are made using a randomization software that chooses one of the two drugs at random. When a patient is being enrolled in the study for an additional site of pathology, they will receive the same drug to which they were initially randomized at each site of pathology and a separate identifier number will be used to track the progress of each site.

5.6 Preparation and Administration of Study Drug

On the date of the planned injection a nurse, resident, fellow or research assistant present at the site and not directly involved in the patient's care will draw up the medication appropriate to the randomized treatment assignment and hand it to the physician who will administer the drug. Both the patient and the treating physician are blinded to the identity of the medication. Patient data will be recorded and kept in

the envelope and only the hand department research assistant or the resident in charge of this project (who will not be directly involved in patient care) will know the identity of the treatment given to the enrolled patients. Because both liquids are clear the contents of the syringes do not need to be covered.

5.7 Prior and Concomitant Therapy

There are no restrictions to concomitant oral medical therapy for subjects enrolled in this study

5.8 Blinding of Study Drug

The study will be a double-blinded prospective randomized controlled trial. Drugs will be stored in the local clinic/office medication storage room. When a patient is enrolled and consented into the study a random envelop (labeled with an identification number) will be opened and in it will contain the group that the patient is randomized to: steroid or ketorolac. On the date of the planned injection a nurse, resident, fellow or research assistant present at the site and not directly involved in the patient's care will draw up the medication and hand it to the physician who will administer the drug. Both the patient and the treating physician are blinded to the identity of the medication. Patient data will be recorded and kept in the envelope and only the hand department research assistant or the resident in charge of this project (who will not be directly involved in patient care) will know the identity of the treatment given to the enrolled patients. Because both liquids are clear the contents of the syringes do not need to be covered

6 Study Procedures

A specific patient population with hand and upper extremity pathologies will be studied including trigger finger, De Quervain's tenosynovitis, and lateral elbow epicondylitis. Patients with trigger finger will be diagnosed clinically by observing symptoms of catching or triggering of the digit with range of motion and tenderness localized to the A1 pulley. Patients with De Quervain's tenosynovitis will be identified clinically as having pain/tenderness at the first dorsal extensor compartment combined with a positive Finkelstein test (pain during full thumb adduction with ulnar deviation of the wrist). Patients with tennis elbow (lateral epicondylitis) will be defined as having lateral elbow pain/tenderness over the extensor origin and/or pain at the lateral epicondyle with resisted wrist extension.

Patients will be consented at the time of their visit with the hand surgeon. Based on inclusion/exclusion criteria it will be determined whether or not to enroll the patient in the study. Consent will be performed by discussing the study with the patient in the privacy of the exam room and having them sign the written consent form that will be IRB approved. There is no payment to the patient for participation and they will be charged for their normal office visit for treatment rendered.

7 Statistical Plan

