9.4 Study Electronic Data

Data will be maintained on a database on a computer which the investigators of this study as well as research assistants have access (however not everyone will see the data due to blinding of the physicians involved in the study). The data will be kept on an NYU research network drive that is password protected. If the data is shared among the investigators it will also be emailed within the NYU email system which is also password protected and encrypted.

All data will be stored for future use. It will take approximately 1-2 years to obtain the number of patients required for the trigger finger arm of the study due to the multitude of patients requiring trigger finger injections in everyday practice. However, it can take longer for the other arms of the study to collect the required amount of patients. The following list explains how this long term data will be handled:

 Data will contain patient names abbreviated with initials of first and last names as well as medical record numbers attached in order to easily obtain more information on the patient in the hospital electronic medical record (EMR)

- Data will be stored indefinitely until it is determined that enough data has been obtained to publish results.
- Data will be kept on an NYU research network drive that the department of hand surgery maintains and is password protected. The resident investigator of this study along with hand department research assistants will have access to the data however any physicians involved in the treatment of these patients will not be able to see the data for blinding purposes.
- Data stored for future use will continue to be maintained in the event a retrospective review of the data is conducted (pending an IRB approval for this as well). At this time it is unknown what this data can also be used for aside from the primary purpose of the study.
- Once the study is complete the results will be shared among physicians. A subject's research
 data will be provided to subjects upon request. Patient will only be told their personal data
 outcomes and the general outcomes of the study as a whole however other patient information
 will be kept from them as per patient confidentiality rules.
- Storage for future use is not optional. This data needs to be stored because it can be used for other research in the future (retrospective reviews, etc).

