10.1 Study Monitoring

For full details on study data and safety monitoring, see the accompanying Data and Safety Monitoring Plan for this study. The responsibility for gathering the data will rest with the individual investigators/health care providers that are directly treating the patients (either at the NYU HJD hand clinic on 23rd street or in the private office of hand attending). Individuals treating patients will be informed to relay any unanticipated problems/concerns/adverse events to the resident research coordinator ([name]). Data will be consolidated and sent to the resident researcher for further evaluation and for monitoring during the course of each patient's length of treatment.

The resident research coordinator ([name]) will ensure data accuracy by monthly asking how the data was collected and ensuring individuals are following proper protocol. In addition, data accuracy will also be maintained with quick training sessions on the study to be conducted at the study site once every 2 month basis. This will be done by the hand research coordinators/assistants, the resident researchers, or the principal investigators/attending involved. Monitoring work will be reviewed at regular intervals with the study Principal Investigator.

Patients that ultimately drop out of the study will be monitored for the course of their regularly scheduled follow-up appointments until there are discharged from the clinic or the care of the attending orthopaedic hand surgeon.

Primary and secondary efficacy endpoints will be monitored. Either patients will have resolution of their symptoms (primary endpoint) with improvement in hand function to their desired satisfaction or they must undergo surgery (secondary endpoint) for correction due to failure of the local soft tissue injection in relieving their symptoms.

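### Patient data are filed in the envelope that names the drug, and the roles that know the drug also have access to the data; the plan describes no safeguard between the two

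*Combined protocol and SAP*

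**What the plan says.** Section 5.5 describes a numbered envelope which, at enrolment, "will be opened and in it will contain the group that the patient is randomized to: steroid or ketorolac"; section 5.8 repeats this. Sections 5.6 and 5.8 then both state: "Patient data will be recorded and kept in the envelope and only the hand department research assistant or the resident in charge of this project", and the sentence continues "who will not be directly involved in patient care) will know the identity of the treatment given to the enrolled patients". The same two sections say who is blinded: "Both the patient and the treating physician are blinded to the identity of the medication".

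On data flow, section 10.1 says the "responsibility for gathering the data will rest with the individual investigators/health care providers that are directly treating the patients". It continues: "Data will be consolidated and sent to the resident researcher for further evaluation", and for monitoring over the patient's course of treatment. A resident research coordinator looks after accuracy by asking each month how the data were collected and whether the protocol is being followed.

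On access, section 9.4 says "The resident investigator of this study along with hand department research assistants will have access to the data", whereas "any physicians involved in the treatment of these patients will not be able to see the data for blinding purposes".

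Section 3.4 has failure rates compared between the two drugs biannually, with a significant difference leading to the study being abandoned. Section 7.2 gives the analysis to a faculty statistician and does not say whether that person is blinded.

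**The concern.** Read together, these sections put the allocation and the patient data in one place and let the same roles reach both. Two weaknesses follow.

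- **Filing.** The people who generate the follow-up data are meant to be blinded or include those who are, yet the place where patient data are kept identifies the drug.
- **Handling.** Once the data leave the clinic, nothing described keeps knowledge of the drug away from those who receive, query and evaluate them.

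The endpoints make this worth attention. Resolution of tenderness, pain on provocation testing (3.2) and improvement to the patient's satisfaction (10.1) all need judgement. Sections 3.2 and 5.1.2 call resolution or surgery the primary endpoint, and the failure comparison in 3.4 can end the study. A decision on an ambiguous or missing record could be coloured by knowing which drug was given.

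**Working it through.** The plan gives no figure on this point, so the check is a comparison of sections.

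1. **What is in the envelope?** By 5.5 and 5.8, the name of the drug. By 5.6 and 5.8, also patient data. No section provides for storing the allocation elsewhere.

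2. **Who knows the drug?** By 5.6 and 5.8, the hand department research assistant or the resident in charge. By 5.6, the nurse, resident, fellow or research assistant who draws up the syringe must know it as well, so the group is wider than the word *only* in the same section implies. The single limit on the assistant or resident is that they take no direct part in patient care. No limit on data handling is stated.

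3. **Who has the data?** By 9.4, the resident investigator and the hand department research assistants. By 10.1, a resident researcher receives the consolidated data for evaluation.

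4. **Do steps 2 and 3 overlap?** Yes, by role. Research assistants of the same department appear in both lists. A resident also appears in both, under different titles (resident in charge, resident investigator, resident researcher, resident research coordinator). The overlap does not depend on these being one person.

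5. **How do follow-up data reach the envelope?** Section 10.1 makes the treating providers responsible for gathering data. Section 9.4 keeps treating physicians from seeing the data for the sake of blinding, which makes most sense if the data can reveal the drug. If providers file their own forms, they handle an envelope that names the drug. If someone else files them, that person either knows the drug already or can learn it. The plan does not say which route applies.

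6. **Does the exposure end at enrolment?** No. A second injection at 4 or 8 weeks must match the randomized group (5.1.2), and a newly enrolled site receives the same drug (5.5). The allocation therefore has to be consulted again after follow-up data exist.

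7. **Where would knowledge of the drug act?** The quickDASH, EQ-5D and pain scale are completed by blinded patients (3.2), and quickDASH and EQ-5D form the primary analysis in 7.2. These are the less exposed outcomes. The more exposed steps are queries, cleaning, decisions on missing data, and deciding whether a record counts as resolved or failed.

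8. **Is a blinded step described anywhere?** The documents mention no blinded data manager, no coded data set and no blinding of the statistician.

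**The case against.** The best defence has five parts.

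- **The protocol claims no more than it delivers.** It defines blinding as covering the patient and the treating physician and never says that data handlers are blinded. A reader might infer that the double-blind claim is contradicted. It is not; this is a missing safeguard.
- **The intent is protective.** Sections 5.6 and 5.8 restrict knowledge of the treatment, and 9.4 bars treating physicians from the data. A reader might infer that physicians will see the allocation. The documents do not show that; they only leave the filing route unstated.
- **No power to edit is given.** A reader might infer that an unblinded resident consolidates and corrects outcomes. Section 10.1 says data are consolidated and sent to the resident researcher, without saying who consolidates, and the accuracy check is a monthly enquiry about process. That queries and classification fall to these staff is an inference from their receiving and evaluating the data.
- **The term is loose.** Patient data is not expressly outcome data. It could mean the treatment record, and other sections place study data in case report forms (8.1), secured records (9.3) and a database (9.4).
- **A relevant document was not available.** Sections 8.4 and 10.1 refer to a separate Data and Safety Monitoring Plan, which may contain data-handling rules.

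All five stand as limits. They do not remove the point: 5.6 and 5.8 as written put allocation and patient data together, the overlap of roles is in the text, and those sections would need correcting even if the monitoring plan adds safeguards.

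**Conclusion.** The point holds as a gap in protection against bias, worth closing. The plan files patient data with the allocation, leaves open how blinded providers' data get there, and gives the roles that know the drug access to the data, with no described barrier for queries, cleaning or the judging of resolution and failure.

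The size of any bias cannot be derived. A figure would need an assumed share of records reclassified because the drug was known, and the documents give no basis for one. A reader might infer an inflated false-positive rate or a shifted mean quickDASH score. The first would rest wholly on assumption, and for the second the documents show no route from a data recipient to a score that a blinded patient completes.

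The conclusion rests on three assumptions: that the envelope holding patient data is the randomization envelope, as the sequence of 5.8 indicates; that patient data include at least some follow-up findings; and that the unseen monitoring plan does not already separate the two.

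**What to change.** Amend 5.6, 5.8, 9.4 and 10.1 as follows.

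- Keep the allocation slip and the drug-preparation record in a separate restricted file, never with patient data. Consult that file for second injections and additional sites.
- Let outcome forms and the database carry only the study identifier, with no field for the drug. Section 9.4 now attaches initials and medical record numbers; these can move to a separate linking list.
- Assign receipt, queries and checking of data to whichever of the two existing roles, assistant or resident, neither holds allocations nor draws up drug, and match the access wording in 9.4 to this. State how forms travel from the treating provider to that person.
- Have the statistician work with coded groups (A/B), including at the six-monthly look, until the data are cleaned and locked. The comparison in 3.4 asks whether failure rates differ, which can be tested without the drug names. Naming the drugs to the statistician at that look would unblind the person who runs the final analysis.

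The cost is revised wording, a second file and a split of tasks between two existing roles. Since 5.6 also allows residents and research assistants to draw up drug, the person checking data must be left out of that duty; the documents do not show whether staffing at each clinic makes this easy. Treatment, visits and sample size do not change.

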7.1 Sample Size Determination

The sample size as stated above was derived by a power analysis. A power analysis indicated that a total sample size of 200 patients randomized equally (1:1 randomization) to each treatment arm (i.e trigger finger, De Quervain's disease, and tennis elbow) without any blocking or stratification would provide 80% statistical power (alpha=.05, beta=0.20) to detect a 10% difference in mean DASH scores between cohorts assuming a common standard deviation of 25% (effect size = 10/25 = 0.4). To account for an estimated 30% loss to follow-up, we plan to enroll a total of 260 patients per treatment arm (i.e. trigger finger, De Quervain's disease, and tennis elbow). In total, there will be approximately 780 patients enrolled among all treatment arms, however we expect the trigger finger group to be the treatment arm that most rapidly enrolls patients.

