3.2 Primary Study Endpoints

The primary endpoint will be functional outcome scores at various follow-up time points using the quickDASH and EQ-5D questionnaire as well as a pain visual analog scale. The primary endpoint for the study would be resolution of symptoms or surgical intervention.

Primary endpoints will depend on the diagnosis of the patient. The following details what will be assessed at each follow-up visit after the initial injection:

- 1) Trigger finger group primary endpoint measures include the resolution of objective triggering and resolution of tenderness at the A1 pulley at subsequent follow-up visits. In addition, patients will be graded based on the Quinnell system to monitor for improvement: 0-normal movement of finger; 1-uneven movement; 2-active correctible locking of digit; 3-passively correctible locking; 4-fixed deformity (15). Patients will complete the quickDASH and EQ-5D questionnaires as well as a pain visual analog scale at each follow-up visit (27).
- 2) De Quervain's tenosynovitis group primary endpoint measures will include objective physical exam findings for the resolution of pain/tenderness over the 1st dorsal extensor compartment and the resolution of pain elicited during the Finkelstein test. In addition, patients will complete the quickDASH and EQ-5D questionnaires as well as a pain visual analog scale at each follow-up visit.
- 3) Lateral epicondylitis of the elbow group primary endpoint measures include the resolution of lateral elbow pain/tenderness over the extensor origin and the resolution of pain at the lateral epicondyle with resisted wrist extension during follow-up examinations. Patient grip strength will also be measured in this cohort using a hand dynamometer. Grip strength will be measured at each follow-up and the average of three tests with 20 second rests in between will be recorded. The contralateral side will also be measured for comparison. Lastly, patients will complete the quickDASH and EQ-5D questionnaires as well as a pain visual analog scale at each follow-up visit.

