3.4 Primary Safety Endpoints

Patients will follow-up after the first injection at 4-weeks, 8-weeks, 12-weeks, and 6 months post injection. During follow-up appointments patients in this study will be monitored based on history and physical exam for any side-effects associated with the administration of local soft tissue injections of dexamethasone or ketorolac.

Patients can withdraw from the study at any time if they wish. Patients whose symptoms do not improve and are candidates for surgery can withdraw from the study and have surgery to correct their specific pathology (secondary endpoint). Patients enrolled in the study will be counseled regarding the likelihood of

the injections working and will be given the opportunity for a second injection at 4 weeks from the time of the first injection if no significant symptoms have resolved. Ultimately it will be up to the patient whether they chose another injection or if they want to resort to a surgical intervention.

Patients who receive ketorolac by randomization as the therapeutic option will have an expected failure rate of approximately 30-50% based on clinical experience and literature review that shows the failure rate of dexamethasone (standard of care) on trigger fingers. The study population will be statistically analyzed biannually to determine if there is a significant difference in the rate of failures between the two groups, however a sizeable study population needs to be established before these conclusions can be drawn. If the rate of failure proves to be statistically significant between the ketorolac and dexamethasone group then the study will have to be ethically abandoned. This determination needs to take into consideration the pretreatment symptoms of the patient since patients who begin treatment with a severe trigger finger (quinnell score=4) have a different prognosis compared to patients who begin with a mild trigger finger (quinnell score=1).

4 Subject Selection and Withdrawal

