7.2 Statistical Methods

Statistics will be conducted by the statistician on faculty with the NYU Hospital for Joint Diseases. Primary analysis will consist of comparisons of the baseline functional scores (quickDASH and EQ5D). These scores will be analyzed and compared to subsequent scores at the various follow-ups (4-weeks, 8-weeks,

12-weeks, 6 months). In addition, changes in scores will also be analyzed between the baseline scores and the subsequent follow-ups. Statistical significance will be determined by p-values less than 0.05.

Secondary analysis will consist of physical exam findings and resolution of symptoms following injections as well as grip or pinch strength using pressure dynamometers to gage improved function following injections as well. In addition, observation of side effects will also be included in the secondary analysis.

8 Safety and Adverse Events

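### Two conflicting primary endpoints are named, and the stated 80% power covers only the score version; resolution or surgery has no power figure and, on the plan's trigger finger failure rate, a detectable difference of about 16 to 20 points

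*Combined protocol and SAP*

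**What the plan says.** **Power.** Section 7.1, repeated in the synopsis, plans "a total sample size of 200 patients randomized equally (1:1 randomization) to each treatment arm", where treatment arm means the disease. The claim made for that number is that it "would provide 80% statistical power (alpha=.05, beta=0.20) to detect a 10% difference in mean DASH scores between cohorts". The SD is taken as 25, which gives a standardised effect of 0.4. The allowance for dropout is put this way: "To account for an estimated 30% loss to follow-up, we plan to enroll a total of 260 patients per treatment arm". No power or precision figure is given for resolution, surgery or failure.

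**Primary endpoint.** The sections disagree:

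- Section 3.2 opens by making functional scores (quickDASH, EQ-5D) and a pain scale primary.
- The same section then states: "The primary endpoint for the study would be resolution of symptoms or surgical intervention". Sections 5.1.2 and 5.4 repeat that sentence.
- Section 7.2 makes quickDASH and EQ-5D the primary analysis and puts resolution of symptoms in the secondary analysis.
- Section 10.1 labels resolution primary and surgery secondary. Sections 3.4 and 4.4 also label surgery secondary.

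**Failure rate.** Section 3.4 gives an "expected failure rate of approximately 30-50" per cent for patients on ketorolac, based on the failure of dexamethasone in trigger finger. No rate is given for De Quervain's tenosynovitis or lateral epicondylitis.

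**Decision rule.** Section 7.2 says: "Statistical significance will be determined by p-values less than 0.05". It gives no margin and no confidence-interval rule, although section 2 asks whether symptom reduction with ketorolac is equal or better.

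**The concern.** A reader who meets an 80% power figure in 7.1, and an endpoint called primary in three separate sections, will naturally join the two. They do not belong together: the calculation is for a difference in mean scores, and a yes/no outcome on the same patients carries much less information.

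The objective adds to the risk. With only a p-value threshold, a non-significant comparison of failure rates could be reported as showing that ketorolac is equal to the standard of care, when the trial had little chance of detecting a moderate excess of failures.

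**Working it through.** **Inputs from the documents.** Alpha 0.05 and power 80% (7.1); difference 10 and SD 25 (7.1); 200 evaluable per disease at 1:1, so 100 per drug (7.1); 260 enrolled with 30% loss (7.1), so 260 × 0.70 = 182, or 91 per drug; failure rate 30 to 50% (3.4).

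**Assumptions not in the documents.** Two-sided test; failure (the converse of resolution) treated as one binary outcome at one time point; the trigger finger rate used as the base rate.

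**Step 1: reproduce the plan's figure.**

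n per drug = 2 × (1.960 + 0.842)² × 25² / 10² = 98.1, rounded up to 99, or 198 in total (a t-test calculation gives 99.1, so 100 per drug).

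Power at 100 per drug: 10 / (25 × √(2/100)) = 2.828; 2.828 − 1.960 = 0.868; power = 80.7%.

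The stated 200 reproduces. A one-sided test would need only 78 per drug, so two-sided is the reading that fits. At 91 per drug the same formula gives about 77%.

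**Step 2: the same patients on a binary outcome.** With p̄ the mean of p1 and p2, d their difference and q = 1 − p:

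z = (d√n − 1.960 × √(2p̄q̄)) / √(p1q1 + p2q2), and power = Φ(z).

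Example, 40% against 50%, n = 100: d√n = 1.000; √(2 × 0.45 × 0.55) = 0.7036, times 1.960 = 1.379; √(0.24 + 0.25) = 0.700; z = −0.541; power = 29.4%.

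The last two columns solve the matching sample-size formula for d at 80% power.

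| Per drug | Base failure rate | Power, 10 points worse | Power, 15 points worse | Detectable worsening (points) | Detectable improvement (points) |
|---|---|---|---|---|---|
| 100 | 30% | 31.6% | 59% | 19.3 | 16.3 |
| 100 | 40% | 29.4% | 57% | 19.7 | 18.3 |
| 100 | 50% | 29.4% | 57% | 19.4 | 19.4 |
| 91 | 30% | 29.2% | 55% | 20.3 | 17.0 |
| 91 | 40% | 27.2% | 53% | 20.7 | 19.0 |
| 91 | 50% | 27.2% | 54% | 20.3 | 20.3 |

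With a continuity correction, the range at 100 per drug becomes 17.2 to 20.7 points.

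**Step 3: size needed for 10 points.** For 40% against 50%: (1.379 + 0.842 × 0.700)² / 0.10² gives 388 per drug. Over the base rates above and both directions, the need is 294 to 388 per drug per disease.

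**Step 4: precision.** The 95% half-width at 100 per drug with equal rates is 1.96 × √(2pq/100): 12.7 points at 30% and 13.9 points at 50%. Identical observed rates of 40% would give an interval of about −13.6 to +13.6 points.

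**Step 5: sensitivity.** If all 260 were evaluable (130 per drug), the detectable difference would be about 14.6 to 17.3 points. Pooling 300 per drug across the three diseases would give about 11 points, but 7.1 sizes each disease separately.

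**The case against.** The strongest reply is that the power calculation matches the planned primary analysis. Section 7.2 makes the functional scores primary and resolution secondary, section 3.2 opens with the scores, and three sections call surgery a secondary endpoint. On that reading nothing is wrongly powered. This stands as far as it goes: a reader might infer that resolution or surgery is the sole primary and that the trial was sized on the wrong endpoint, but the documents do not support that. What remains is a contradiction with only one side powered.

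Other limits also stand:

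- **The binary outcome is constructed here.** Resolution and surgery are opposite outcomes, no time point is fixed, and a patient with persisting symptoms and no surgery is unclassified.
- **The base rate is for trigger finger only.** A reader might apply the 16 to 20 points to all three diseases; for the other two that is an assumption.
- **The 10-point benchmark is illustrative.** The plan's 10% is a score difference, not a difference in failure rates.
- **A 15-point excess is not usually missed.** Power is 57 to 59% at 100 per drug and 53 to 55% at 91, so it would be detected somewhat more often than not. Only near 10 points is a miss the likely result.
- **The width of the 30 to 50% range is not an error.** It resembles the detectable difference in size, but uncertainty about a base rate is not an effect between drugs.
- **The failure comparison in 3.4 is a periodic check under the safety endpoints.** It does not make failure rate the primary efficacy test.

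None of this supplies the missing statement of which primary the 80% covers, or a figure for the endpoint that three sections call primary.

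**Conclusion.** The point holds in limited form. The documents name two incompatible primary endpoints, and the 80% power belongs to only one of them, a mean DASH difference of 10 with SD 25. That calculation is itself correct for 200 evaluable patients.

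For resolution or failure, 100 per drug would miss a 10-point increase in failures about 68 to 71% of the time. They reach 80% power at about 19 to 20 points for a worsening or 16 to 19 for an improvement. After the plan's own 30% loss, these become about 20 to 21 and 17 to 20 points. The confidence interval on the difference would extend about 13 to 14 points either side at 100 per drug.

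These sizes rest on a two-sided test, a single binary outcome at one time point, and the trigger finger failure rate. The plan fixes neither of the first two and gives the third for one disease only. The contradiction, and the absence of any power figure for resolution or surgery, depend on none of these assumptions.

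**What to change.** - **Sections 3.2, 5.1.2, 5.4, 7.2 and 10.1, and the surgery labels in 3.4 and 4.4:** reconcile them so that one primary endpoint is named, consistent with 7.1 and 7.2. The score endpoint is the one that was powered.
- **Section 7.1 and the synopsis:** state that the 80% applies only to the mean DASH score, and that SD 25 is assumed to carry over to the quickDASH that the trial administers. Add that, for resolution or failure, 200 evaluable patients per disease detect about 16 to 20 points with 80% power. Label this as an assumption based on the trigger finger failure rate, a two-sided test and one binary outcome at a stated time point.
- **Section 7.2:** report the failure-rate difference between drugs for each disease with a 95% confidence interval, and state that a non-significant comparison does not by itself support equality.

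The cost is wording only, with no change in enrolment. The downside is that a stated figure becomes less favourable.
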